2.7.4 Judgement of causal relationship with drugs

Indicators of causal judgement in the determination of adverse events include: 1. whether the time of initiation of the drug is reasonably related to the appearance of the suspected adverse reaction; 2. whether the suspected adverse reaction corresponds to the type of adverse reaction known for the drug; 3. whether the suspected adverse reaction can be explained by the effect of the combination of the drugs, by the patient's clinical condition, or by the effect of other therapies; 4. whether the suspected adverse reaction disappears or is alleviated by discontinuation or reduction of the dose; and 5. whether the suspected adverse reaction disappears or is alleviated after re-exposure to the drug. Whether the same reaction recurs after re-exposure to the suspected drug. Criteria for determining causality: according to the above 5 judgement indicators in order (Table 3). Based on Table 4, determine the relationship between the following 5 levels of adverse events and the medicinal product: 1-certainly related, 2-maybe related, 3-cannot be determined, 4-maybe not related, 5-certainly not related. The incidence of adverse events was calculated using the total number of cases 1+2+3 as the numerator and all the enrolled cases available for adverse event evaluation as the denominator.

Table 3. Adverse event causation judgements.

Judgement results	Judgement indicators				
	1	2	3	4	5
Certainly relevant	+	+	-	+	+
Possibly relevant	+	+	-	+	?
Undetermined	+	+	±	±	?
Possibly irrelevant	+	-	±	±	?
Definitely irrelevant	-	-	+	-	-

Description: + affirmative, - negative, ± difficult to affirm or deny, ? Circumstances unknown.

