2.7.9 Reporting and Handling of Adverse Events

The occurrence of any adverse event, such as the subjective discomfort of patients and abnormal laboratory tests, should be taken seriously, carefully analysed, and immediate measures should be taken to protect the safety of the subjects. Record in detail in the CRF form and retest in 24 hours

and 7 days and 14 days as appropriate. Record its persistence, regression and disappearance. Handling of Serious Adverse Events: Any serious adverse event that occurs during the trial must be reported immediately to the Medical Ethics Committee of the lead unit or the principal investigator by completing the Serious Adverse Event Report Form (SARF), and in the case of serious adverse reactions, to the State Food and Drug Administration (SFDA) within 24 hours. Notify the telephone number and contact person of the unit listed in the CRF form. When a patient has an emergency, the principal investigator of the research unit can open the emergency letter of the corresponding number taken by the patient (but there must be two witnesses present, and make corresponding records), according to the drug and the symptoms of the appropriate treatment, and notify the clinical monitor of the results of the treatment, and the researcher should be recorded in the case report form in detail on the reason for the breakthrough of blinding, date, treatment, results and sign. All adverse events should be followed up until they are properly resolved or the condition is stabilised. The method of follow-up can be inpatient, outpatient, home visit, telephone, or newsletter, depending on the type and severity of the adverse event.

Statistical Analysis

Statistical software such as SPSS 25.0 and GraphPad Prism were used for data analysis and statistical graphing in this study, with a test level of α taken as 0.05 and two sided test, giving point estimates and 95% confidence intervals.

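### Table 3 gives no causality class to an event with plausible timing that another therapy clearly explains, or to one with implausible timing and no rechallenge, and indicator 5 is worded in two opposite directions

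*Protocol*

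**What the plan says.** Protocol section 2.7.4 lists five indicators and says that causality is judged from them by Table 3. The three that matter most here are:

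- Indicator 1, timing: "whether the time of initiation of the drug is reasonably related to the appearance of the suspected adverse reaction".
- Indicator 3, another explanation: "whether the suspected adverse reaction can be explained by the effect of the combination of the drugs", by the patient's condition, "or by the effect of other therapies".
- Indicator 5, rechallenge: "whether the suspected adverse reaction disappears or is alleviated after re-exposure to the drug". The next sentence reads "Whether the same reaction recurs after re-exposure to the suspected drug".

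The key under Table 3 gives '±' the meaning that the point can be neither affirmed nor denied, and '?' the meaning that the circumstances are unknown. The same section makes classes 1, 2 and 3 (certainly related, maybe related, cannot be determined) the numerator of the adverse event incidence.

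Section 1.1 gives chemotherapy to both arms alongside granules or placebo. Section 2.2 describes it as platinum-based, in four cycles of three weeks. Section 2.3 sets the granule period at six months.

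**The concern.** An event during chemotherapy can follow the start of the granules at a plausible interval and also be clearly explained by the chemotherapy. That is '+' on indicator 1 and '+' on indicator 3. Section 2.7.1 asks for attention to the blood, digestive and urinary systems when the test drug is assessed, so indicator 2 could be '+' as well. If Table 3 has no row for such an event, the Protocol does not say whether it enters the stated incidence, and each site has to decide for itself.

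The two wordings of indicator 5 raise a second problem. Under one of them, a reaction that returns on re-exposure scores '-' and cannot reach the class "Certainly relevant".

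**Working it through.** No sample size, power or error rate is involved. The check matches answer patterns to rows. I take the five numbered levels in section 2.7.4 to be the five rows of Table 3 in order.

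| Row | 1 | 2 | 3 | 4 | 5 | In numerator |
|---|---|---|---|---|---|---|
| Certainly related | + | + | - | + | + | yes |
| Possibly related | + | + | - | + | ? | yes |
| Undetermined | + | + | ± | ± | ? | yes |
| Possibly unrelated | + | - | ± | ± | ? | no |
| Definitely unrelated | - | - | + | - | - | no |

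**Step 1: all patterns.** Let indicators 1 to 4 each take '+', '-' or '±', and indicator 5 take '+', '-' or '?'. That gives 3 × 3 × 3 × 3 × 3 = 243 patterns. Read by the key, the five rows cover 5.

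**Step 2: plausible timing, clearly explained by another therapy.** Four rows have '+' on indicator 1. Their entries on indicator 3 are '-', '-', '±' and '±'. The only row with '+' on indicator 3 is "Definitely irrelevant", which needs '-' on indicator 1. With indicators 1 and 3 fixed at '+', 3 × 3 × 3 = 27 patterns remain, and 0 have a row.

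**Step 3: implausible timing, no rechallenge.** With indicator 1 '-' and indicator 5 '?', again 3 × 3 × 3 = 27 patterns remain. The only row with '-' on indicator 1 needs '-' on indicator 5, so 0 have a row.

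**Step 4: looser readings.**

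- '?' in a row read as any answer: Step 2 stays at 0 of 27.
- '±' in a row read as any answer: indicator 2 may be '+' or '-', indicator 4 anything, and indicator 5 must be '?'. That gives 2 × 3 × 1 = 6 of 27.
- Both read as any answer: 2 × 3 × 3 = 18 of 27.
- Step 3 stays at 0 of 27 throughout, because the last row has neither '±' nor '?' to relax.

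Under the '±' reading, an event with no rechallenge goes to undetermined (counted) if indicator 2 is '+', and to possibly unrelated (not counted) if it is '-'. The same reading makes '+ + - + ?' fit two rows, possibly related and undetermined.

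**Step 5: indicator 5.** The top row needs '+' and the bottom row '-'. Under the recurrence wording, '+' means that the reaction came back, which fits the top row. Under the easing wording, '+' means that it went away on re-exposure. A reaction that came back would then score '-', and '+ + - + -' has no row. The other three rows carry '?', so the conflict touches only the two extreme classes. It plays no part in Steps 2 and 3.

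**The case against.** **The easing wording is a slip.** This is likely. It repeats the phrase of indicator 4, the next sentence asks the proper rechallenge question, and Table 3 fits only that sentence. But both sentences stand in the current text, and removing one costs nothing.

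**'±' may have been meant as either sign.** On that reading every plausible-timing pattern without rechallenge and with a definite answer on indicator 2 has a row, which suggests it may be how the table was meant to be used. The printed key says otherwise, and the reading creates an overlap. An investigator who is truly unsure about chemotherapy can enter '±' on indicators 3 and 4 and reach a row. The gap is therefore limited to events that another therapy clearly explains, plus the implausible-timing events of Step 3.

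**Little is lost in practice.** Section 2.7.2 has every event recorded whether related or not. Allocation is double-blind and stratified by centre (section 2.1), and both arms receive chemotherapy, so differing site habits need not bias the comparison. This stands and limits the consequence to the absolute related incidence.

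A reader might infer more than the Protocol supports:

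- *That the commonest events cannot be classified.* The Protocol gives no adverse event frequencies.
- *That the pattern counts are a rate.* They treat all sign combinations alike and say nothing about how many events are affected.
- *That regulatory reporting depends on Table 3.* Section 2.7.9 has every serious adverse event reported to the ethics committee or principal investigator whatever its cause. Only the further step, "in the case of serious adverse reactions, to the State Food and Drug Administration", speaks of reactions, and it is not tied to the Table 3 classes.

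**Conclusion.** The point holds in a limited form. Read by its own key, Table 3 has no row for plausible timing with a clear explanation by another therapy, and none for implausible timing without rechallenge. Indicator 5 carries two opposite wordings, of which only recurrence fits the table. This is not detail left for a later document, because the Protocol itself fixes both the rule and the numerator.

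The size cannot be put as a number of events. The gap is 0 of 27 patterns in each group, and what it affects is mainly the absolute related incidence. The conclusion assumes that the printed key governs and that granules and chemotherapy overlap in time, as section 1.1 implies. The correction should be made, but the point does not touch the primary analysis of disease-free survival.

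**What to change.** In section 2.7.4:

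1. Delete the easing wording of indicator 5 and keep the question whether the same reaction recurs on re-exposure.
2. Allow '?' for indicator 5 in the last row of Table 3.
3. State one class in advance, the same at all sites, for events with indicators 1 and 3 both '+', and likewise for any other unlisted pattern. Do not send them all to class 3 by default: that would count events clearly explained by chemotherapy as related to the granules, and nothing in the Protocol shows that the rise would be small.
4. Report all-cause adverse event incidence by arm, from the events already recorded under section 2.7.2, beside the incidence from classes 1 to 3. The safety comparison then does not depend on the classification.

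The cost is a few lines of text, an edit to the CRF completion guide and a small amount of extra tabulation. No new data are needed.

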2.7.2 Observation and recording of adverse events

Observation and recording: The investigator should carefully observe any adverse events occurring in the subjects during the clinical study period, and require the subjects to truthfully reflect the changes in their condition after the administration of the drug, avoiding induced questions. While observing the efficacy, pay attention to the observation of adverse events or unanticipated toxic side effects (including symptoms, signs and laboratory tests). Regardless of whether the adverse event is related to the test drug or not should be recorded in detail in the CRF form, including the time of the appearance of the adverse event, symptoms, signs, degree, duration,

laboratory test indexes, treatment methods, after, results, follow-up time, etc., and should be recorded in detail in the case of the combined use of medication, in order to analyse the relevance of the adverse event to the test drug, the record should be signed and dated. Medical treatment of subjects: When adverse events are detected, the investigator may take necessary treatment measures according to the condition, such as adjusting the dosage, temporarily interrupting the medication, etc., and decide whether to terminate the trial. In the event of serious adverse events, the unit undertaking the trial study must immediately take the necessary treatment measures to protect the safety of the subjects.

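### The protocol's only defined incidence of adverse events counts causality classes 1 to 3, so it is a suspected-reaction rate under the wrong name, and no counted row of its causality table admits a new type of event

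*Protocol*

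**What the plan says.** Protocol section 2.7.4 sets up five causality indicators, a decision table (Table 3) and five causality classes, and then fixes a rate. Its numerator is given as: "The incidence of adverse events was calculated using the total number of cases 1+2+3 as the numerator". Its denominator is "all the enrolled cases available for adverse event evaluation as the denominator". The two classes left out of the numerator are "4-maybe not related, 5-certainly not related".

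Indicator 2 asks "whether the suspected adverse reaction corresponds to the type of adverse reaction known for the drug". The legend to Table 3 gives the ± symbol the meaning "difficult to affirm or deny" and uses the question mark for unknown circumstances. The instruction for assigning classes reads: "Based on Table 4, determine the relationship between the following 5 levels of adverse events and the medicinal product". No table numbered 4 appears in the protocol.

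Section 2.7.2 sets a wider scope for recording: "Regardless of whether the adverse event is related to the test drug or not should be recorded in detail in the CRF form". It also tells investigators to "pay attention to the observation of adverse events or unanticipated toxic side effects (including symptoms, signs and laboratory tests".

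**The concern.** An adverse-event incidence is ordinarily read as covering all events. The protocol records on that basis, but the rate it defines filters events by judged cause. A reader of the trial report would take the filtered figure for the full one.

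The filter matters in this design. Both arms receive platinum chemotherapy (section 2.2) and the control is a blinded placebo (section 1.1). Randomisation and blinding allow an all-cause rate to be compared between arms without deciding the cause of each event. The defined rate gives that advantage up. If the formula made a toxicity typical of chemotherapy more frequent, investigators could attribute the extra events to chemotherapy, and any placed in class 4 or 5 would drop out.

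Table 3 raises a separate question: whether an unexpected reaction to the formula could enter the numerator at all.

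**Working it through.** **1. The definition against the recording rule.** Section 2.7.2 covers all events (classes 1 to 5). The rate in section 2.7.4 covers classes 1 to 3. The difference is every patient whose only events are in class 4 or 5. This step does not depend on Table 3.

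**2. Is another incidence defined?** Section 2.6.3 lists adverse events as a safety indicator to be recorded, without a rate. Sections 2.7.2 and 2.7.9 cover recording, handling and reporting. The Statistical Analysis section gives general methods for count data (rates, chi-square or Fisher tests) without an adverse-event numerator. The 1+2+3 rate is the only one defined.

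**3. Table 3 as printed** (columns 1 to 5 are the indicators):

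| Class | 1 | 2 | 3 | 4 | 5 | In numerator |
|---|---|---|---|---|---|---|
| 1 certainly relevant | + | + | − | + | + | yes |
| 2 possibly relevant | + | + | − | + | ? | yes |
| 3 undetermined | + | + | ± | ± | ? | yes |
| 4 possibly irrelevant | + | − | ± | ± | ? | no |
| 5 definitely irrelevant | − | − | + | − | − | no |

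Every counted row has + on indicator 2. The only rows with − on indicator 2 are the two uncounted ones.

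**4. Enumeration.** Allow + or − on indicators 1 and 2; +, − or ± on indicators 3 and 4; and +, − or ? on indicator 5. That gives 2 × 2 × 3 × 3 × 3 = 108 patterns. Two readings are possible.

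- *Strict*: ± and ? in a row accept only that answer. Each row then fits one pattern, so 5 are classed and 108 − 5 = 103 are not.
- *Loose*: ± and ? in a row accept any answer, and where rows overlap the lower-numbered class applies. Class 1 takes 1, class 2 takes 3 − 1 = 2, class 3 takes 27 − 3 = 24, class 4 takes 27 and class 5 takes 1. The total is 55, leaving 108 − 55 = 53 unclassed, all with − on timing (indicator 1).

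| Patterns | Number | Strict | Loose |
|---|---|---|---|
| New type, plausible timing (+, −, any, any, any) | 3 × 3 × 3 = 27 | 1 in class 4, 26 unclassed | 27 in class 4 |
| of which counted | | 0 | 0 |
| Known type, other explanation available (+, +, +, any, any) | 3 × 3 = 9 | 9 unclassed | 9 in class 3 |
| of which counted | | 0 | 9 |

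One example is an event of a new type with plausible timing, no other explanation, improvement on withdrawal and recurrence on re-exposure: (+, −, −, +, +). It fits no row on the strict reading and is class 4 on the loose one. Neither is counted.

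**5. Sensitivity.** Allowing all four symbols on every indicator gives 4⁵ = 1024 patterns. Of these, 4³ = 64 are new-type with plausible timing. Strictly, 1 is class 4 and 63 are unclassed; loosely, all 64 are class 4. Again none is counted.

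**The case against.** The strongest reply is that this is a labelling slip. The rate sits in a section on causality whose indicators speak of suspected reactions, and changing one word, from events to reactions, would make it correct. An all-cause table by arm is the kind of output an analysis plan usually fixes, that plan is not at hand, and the data for it are secured. The protocol does not say that 1+2+3 is the only rate to be reported. Attribution is made blind, so misattribution should be similar in the two arms.

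Much of this is fair. The 1+2+3 rate is a legitimate quantity, and all-cause rates can be derived from what is recorded. But the protocol does not leave the matter open: it states a numerator and a denominator under the name of adverse-event incidence. An analysis plan that follows it inherits the error, and one that reports all events under the same name contradicts it. Blind attribution guards against judging the two arms differently. It does not bring back real extra events that are attributed to chemotherapy and left out.

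On Table 3, the pattern counts describe the table and give no indication of how often each pattern would occur. The gap for (+, +, +) arises only on the strict reading. So does any uncertainty between class 3 and class 4 for a new-type event answered − on indicator 2. An investigator might also depart from the table by judgement. The result for new-type events, however, is the same on both readings. The reference to Table 4 is clerical: two tables are numbered 1, so the causality table is the fourth in sequence, and its five rows match the five classes.

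**Conclusion.** The point holds and should be corrected. The defined incidence is a suspected-reaction rate under an adverse-event label. It falls below the real incidence whenever at least one patient has only class 4 or 5 events. By how much cannot be computed from the protocol.

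Separately, if Table 3 is applied as written, 0 of 27 patterns for a plausibly timed new-type event enter the numerator on either reading, although section 2.7.2 asks investigators to watch for unanticipated effects. On the strict reading 103 of 108 patterns have no stated class, and the protocol does not say how to class them. One investigator could choose class 3, which is counted, and another class 4, which is not.

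The harm is limited to this reported rate. All events stay on the case report form, any serious adverse event is reported whatever its cause (section 2.7.9), and the general between-group tests could be applied to all recorded events. The first conclusion rests only on the wording of sections 2.7.2 and 2.7.4. The second assumes that classes are assigned from Table 3, as section 2.7.4 directs.

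**What to change.** **Rate.** Define the incidence of adverse events over all recorded events, classes 1 to 5, by arm, with the stated denominator. Keep the 1+2+3 rate in a separate table labelled as suspected drug-related adverse reactions. This costs one sentence and one extra table from data already collected. Reported incidences will look higher in both arms.

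**Causality table.** Correct the reference to Table 4. Reconcile Table 3 with section 2.7.2 so that every answer pattern has a stated class, including new-type events and known-type events that another therapy could explain. This costs more: investigators must be retrained, and the sponsor must check whether reclassification changes which events count as serious adverse reactions for the 24-hour report in section 2.7.9.

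The first change does not depend on the second and can be made at once.

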2.7.9 Reporting and Handling of Adverse Events

The occurrence of any adverse event, such as the subjective discomfort of patients and abnormal laboratory tests, should be taken seriously, carefully analysed, and immediate measures should be taken to protect the safety of the subjects. Record in detail in the CRF form and retest in 24 hours

and 7 days and 14 days as appropriate. Record its persistence, regression and disappearance. Handling of Serious Adverse Events: Any serious adverse event that occurs during the trial must be reported immediately to the Medical Ethics Committee of the lead unit or the principal investigator by completing the Serious Adverse Event Report Form (SARF), and in the case of serious adverse reactions, to the State Food and Drug Administration (SFDA) within 24 hours. Notify the telephone number and contact person of the unit listed in the CRF form. When a patient has an emergency, the principal investigator of the research unit can open the emergency letter of the corresponding number taken by the patient (but there must be two witnesses present, and make corresponding records), according to the drug and the symptoms of the appropriate treatment, and notify the clinical monitor of the results of the treatment, and the researcher should be recorded in the case report form in detail on the reason for the breakthrough of blinding, date, treatment, results and sign. All adverse events should be followed up until they are properly resolved or the condition is stabilised. The method of follow-up can be inpatient, outpatient, home visit, telephone, or newsletter, depending on the type and severity of the adverse event.

Statistical Analysis

Statistical software such as SPSS 25.0 and GraphPad Prism were used for data analysis and statistical graphing in this study, with a test level of α taken as 0.05 and two sided test, giving point estimates and 95% confidence intervals.

Lung cancer is the leading malignant tumour in China in terms of deaths, and metastasis is the key cause. With the advances in diagnostic and treatment technologies (e.g., postoperative chemotherapy, targeted therapy, immunotherapy), the survival time and quality of life of postoperative patients have been improved to some extent. However, there is still a lack of effective standardised diagnostic and treatment protocols for postoperative radical lung cancer patients with negative driver gene expression, which has led to this specific group of patients becoming a challenge in the clinic that restricts the improvement of the overall efficacy of lung cancer, and at the same time, causes the society and families to incur huge medical costs.

This research programme inherits the theoretical advantages of Chinese medicine's "the Holistic Concept" and the thought of "Preventive Treatment of Disease", inherits the academic thought of "Treating Cancer by Reforcing Healthy Qi", and gives full play to the advantages of systems biology, Precision medicine and Chinese medicine. Based on the theory of "Deficiency of Vital Qi and Hidden Toxin", the research target is located in IIA-IIIA stage IIA-IIIA lung cancer patients who are negative for the expression of driver genes after radical surgery, and carry out a multi-centre clinical study on the combination of chemotherapy with Chinese medicine to prevent and control the recurrence and metastasis of IIA-IIIA stage IIA-IIIA driver gene-negative NSCLC after radical surgery. The study clarified the comprehensive efficacy of TCM in regulating the internal environment of the body's immune function state to reduce recurrence and metastasis, with a view to obtaining high-level evidence-based medical evidence and forming a standardised diagnostic and treatment protocol of TCM for preventing and treating recurrence and metastasis of postoperative cancer that can be promoted and applied, so as to promote the improvement of the therapeutic efficacy of postradical treatment of lung cancer patients. Secondly, based on the results of the study, the advantageous population of TCM for the prevention of recurrence and metastasis was screened out by combined MRD detection, and histopathology, circulating tumour cells, tumour-associated exosomes, immune indexes and other related indexes of postoperative patients with stage IIA-IIIA lung adenocarcinoma who were negative for the expression of driver genes were detected, and the therapeutic efficacy prediction model of postoperative patients with stage IIA-IIIA lung adenocarcinoma who were negative for the expression of driver genes was jointly established, so as to improve the precise treatment level of lung cancer after radical surgery and promote the overall prevention and control efficiency of lung cancer.

Acknowledgments

We are grateful to Staff of the Clinical Research Centre of Shanghai Municipal Hospital of Traditional Chinese Medicine, Shanghai University of Traditional Chinese Medicine for his expert assistance with the writing of the study protocol.

List of Abbreviation

TCM, traditional Chinese medicine

NCCN, National Comprehensive Cancer Network

DFS, disease-free survival

OS, overall survival

MRD, minimal residual disease

QoL, quality of life

SII, systemic immune- inflammation index

PIN, prognostic nutritional index
NSCLC, non-small cell lung cancer
PNI, pharmaceutical news index
TBIL, blood bilirubin,
AST, aspartate aminotransferase
CREA, creatinine
WBC, white blood cell count
PLT, platelet count
HCT, erythrocyte pressure
PS, performance status.
ALT, alanine aminotransferase
AST, aspartate aminotransferase
 γ -GT, glutamyl transpeptidase
BUN, urea nitrogen
UPr, urinary protein
SPSS, Statistical Product and Service Solutions
CRFs, the case report forms
EDC, electronic case information system
DSMB, data safety and monitoring board
TNM, tumor node metastasis
TNF, tumour necrosis factor
SARF, the Serious Adverse Event Report Form
SFDA, the State Food and Drug Administration
FAS, full analysis set
PPS, compliance with the protocol set
HR, the hazard ratio
ITT, Intention-to-treat
GCP, Good Clinical Practice

Availability of Data and Material

The results of our study will be presented at relevant scientific conferences and/or magazines. The raw trial data will be published on the China Clinical Trial Registration website within 6 months of trial completion.

Ethics Approval and Consent to Participate

The trial will be conducted in accordance with Good Clinical Practice (GCP) guidelines; it will be supervised and managed by The Ethics Committee of Shanghai Municipal Hospital of Traditional Chinese Medicine, Shanghai University of Traditional Chinese Medicine. The investigational plan was approved by Shanghai Municipal Hospital of Traditional Chinese Medicine, Shanghai University of Traditional Chinese Medicine (approval no.: 2023SHL-KY-19-01). All participants would sign the informed consent before joining the trial.

References

[1] Sharma R. Mapping of global, regional and national incidence, mortality and mortality-to-incidence ratio of lung cancer in 2020 and 2050[J]. Int J Clin Oncol,2022,27(4):665-675.

